7.8 LONG TERM FOLLOW-UP ASSESSMENTS

Trial participants will not be monitored after the active treatment phase has finished (24 hours post aspirin ingestion).

A letter informing the GP of the participation in the study will be sent explaining study procedures and highlighting a need to resume clinically recommended aspirin dose at the end of the trial.

7.9 WITHDRAWAL CRITERIA

Participants will be free to withdraw (discontinue his or her participation) from the study at any point of the trial without giving a reason. The investigator team will reserve the right to terminate participation where patient safety or trial integrity may be compromised.

Data collected prior to withdrawal from the trial will not be used and samples will be destroyed.

Considering time demands of the trial, anticipated withdrawal / attrition rate is 25% and we plan to recruit up to 18 participants to reach required sample size of 14 participants (see sample size section).

7.10 STORAGE AND ANALYSIS OF CLINICAL SAMPLES

At every collection time point one 5 mL sample of blood to be obtained using serum separator tubes (BDSST II Advance).

7.10.1 THROMBOXANE B₂ SAMPLE

Please see SOP for processing manual.

Remaining of samples will be transferred to the Newcastle Utero-placental Tissue bank in cases where participants gave consent to keep the samples. Alternatively, samples will be destroyed in line with organisational guideline for clinical waste incineration.

7.10.2 SALICYLIC ACID SAMPLE

Salicylic Acid samples will be processed in Institute of Cellular Medicine, Newcastle University. Tracked using an Achiever system and securely stored within the ICM freezers.

Please see SOP for processing manual.

Samples will be stored and analysed upon completion of the trial.

Remaining of samples will be transferred to the Newcastle Utero-placental Tissue bank in cases where participants gave consent to keep the samples. Alternatively, samples will be destroyed in line with organisational guideline for clinical waste incineration.

7.11 END OF TRIAL

End of trial is defined a last sample processed.

The sponsor will notify the MHRA of the end of a clinical trial within 90 days of its completion.

8 TRIAL TREATMENTS

8.1 NAME AND DESCRIPTION OF INVESTIGATIONAL MEDICINAL PRODUCT(S)

Aspirin 75mg dispersible tablets.

Each tablet contains 75 mg acetylsalicylic acid.

8.2 REGULATORY STATUS OF THE DRUG

Not licensed for use in pregnancy, however widely clinically accepted in doses 75 mg and 150 mg (6) .

8.3 PRODUCT CHARACTERISTICS

The SmPC for a generic common brand of aspirin (appendix 2) will be used for reference of safety data and product characteristics due to the large number of brands of aspirin stocked by the dispensing pharmacy.

8.4 DRUG STORAGE AND SUPPLY

As this is a Type A risk adaptive approach study there will be no accountability, segregated storage, temperature monitoring or labelling compliant with annex 13 performed for this study IMP.

8.5 PREPARATION AND LABELLING OF INVESTIGATIONAL MEDICINAL PRODUCT

As per 8.4, no labelling compliant with annex 13 will be expected for this IMP. Preparation and labelling is not applicable for this trial as participants will be obtaining clinically prescribed medication in line with the Trust's practice. This may take place before or after consent procedure to enter the trial.

8.6 DOSAGE SCHEDULES

Study participant will be expected to take 75 mg of aspirin (1 tablet) on one occasion and 150 mg of aspirin (2 tablets) on the other. Those doses will be taken 1 week apart to account to 7 day washout period.

8.7 DOSAGE MODIFICATIONS

Dosage modifications will not be permitted.

Participants will be advised to continue with clinically indicated therapy at the last study visit.

8.8 KNOWN DRUG REACTIONS AND INTERACTION WITH OTHER THERAPIES

Methotrexate at doses >15 mg/week is contraindicated to be taken with aspirin. However use of Methotrexate is contraindicated in pregnancy and we do not anticipate any pregnant participants on Methotrexate.

SHORT TITLE: DORA

EudraCT number: 2021-00071-36

Use of aspirin in patients receiving uricosuria agents, other anticoagulants and anti-platelet agents, selective serotonin reuptake inhibitors, sulfonyleureas, digoxin and lithium, diuretics, antihypertensives, NSAIDs, acetazolamide), systemic corticosteroids, ibuprofen, cyclosporine, tacrolimus, antacids, alcohol will be carefully considered by a medical team. Please note some of the above medications will be contraindicated in pregnancy.

8.9 CONCOMITANT MEDICATION

Pregnant women on anticoagulants and other anti-platelet agents will not be able to enter the trial.

8.10 TRIAL RESTRICTIONS

All participants who were prescribed and accepted aspirin therapy and do not fall in any of the exclusion category are permitted to enter the trial.

8.11 ASSESSMENT OF COMPLIANCE WITH TREATMENT

Trial participant will be observed by the research delivery team at the time of ingestion of both doses of aspirin during visit 1 and visit 3.

SHORT TITLE: DORA

EudraCT number: 2021-00071-36

9 PHARMACOVIGILANCE

9.1 DEFINITIONS

Term	Definition
Adverse Event (AE)	Any untoward medical occurrence in a participant to whom a medicinal product has been administered, including occurrences which are not necessarily caused by or related to that product.
Adverse Reaction (AR)	
An untoward and unintended response in a participant to an investigational medicinal product which is related to any dose administered to that participant.
 
The phrase "response to an investigational medicinal product" means that a causal relationship between a trial medication and an AE is at least a reasonable possibility, i.e., the relationship cannot be ruled out.
 
All cases judged by either the reporting medically qualified professional or the Sponsor as having a reasonable suspected causal relationship to the trial medication qualify as adverse reactions. It is important to note that this is entirely separate to the known side effects listed in the SmPC. It is specifically a temporal relationship between taking the drug, the half-life, and the time of the event or any valid alternative etiology that would explain the event.

Serious Adverse Event (SAE)	
A serious adverse event is any untoward medical occurrence that:
 
 results in death is life-threatening requires inpatient hospitalisation or prolongation of existing hospitalisation results in persistent or significant disability/incapacity consists of a congenital anomaly or birth defect 
Other 'important medical events' may also be considered serious if they jeopardise the participant or require an intervention to prevent one of the above consequences.
 
NOTE: The term "life-threatening" in the definition of "serious" refers to an event in which the participant was at risk of death at the time of the event; it does not refer to an event which hypothetically might have caused death if it were more severe.

EudraCT number: 2021-000071-36

SHORT TITLE: DORA

Serious Adverse Reaction (SAR)
	
An adverse event that is both serious and, in the opinion of the reporting Investigator, believed with reasonable probability to be due to one of the trial treatments, based on the information provided.


Suspected Unexpected Serious Adverse Reaction (SUSAR)
	
A serious adverse reaction, the nature and severity of which is not consistent with the information about the medicinal product in question set out in the reference safety information:
 
In the case of a product with a marketing authorisation, this could be in the summary of product characteristics (SmPC) for that product, so long as it is being used within its license. If it is being used off label an assessment of the SmPC’s suitability will need to be undertaken.
 
in the case of any other investigational medicinal product, in the investigator’s brochure (IB) relating to the trial in question

NB: to avoid confusion or misunderstanding of the difference between the terms “serious” and “severe”, the following note of clarification is provided: “Severe” is often used to describe intensity of a specific event, which may be of relatively minor medical significance. “Seriousness” is the regulatory definition supplied above.

Detailed guidance can be found here:

http://ec.europa.eu/health/files/eudralex/vol-10/2011_c172_01/2011_c172_01_en.pdf

9.2 OPERATIONAL DEFINITIONS FOR (S)AEs

Use of aspirin in pregnancy is outside of the licensed indication. Although it will be used in a clinically accepted doses with high safety profile, we will record all (S) AE’s and (S) AR’s. All (S) AE’s and (S) AR’s will be assessed by PI/CI prior to reporting.

All pre-existent conditions will be exempt from reporting.

9.3 RECORDING AND REPORTING OF SAEs, SARs AND SUSARs

Safety monitoring will be performed during the trial visits and end at 24 hours post last study dose ingestion (i.e., end of the participation) due to short half-live of aspirin and fast elimination.

Long term follow up will not be performed as teratogenicity of a single low dose of aspirin is not recognized.

Safety reporting form will be completed by a member of the research team, assessed by PI/CI and reported to the Sponsor’s team

Where a participant withdraws consent safety assessments will be performed at 24 hours post aspirin ingested at the research visit.

EudraCT number: 2021-000071-36

SHORT TITLE: DORA

All SAEs occurring from the time start of trial treatment until 24 hours post cessation of trial treatment must be recorded on the safety assessment form and e-mailed to the Sponsor within 24 hours of the research staff becoming aware of the event. Once all resulting queries have been resolved, the Sponsor will request the original form should also be posted to the Sponsor and a copy to be retained on site.

For each SAEs the following information will be collected:

- full details in medical terms and case description
- event duration (start and end dates, if applicable)
- action taken
- outcome
- seriousness criteria
- causality (i.e. relatedness to trial drug / investigation), in the opinion of the investigator
- whether the event would be considered anticipated

Any change of condition or other follow-up information should be e-mailed to the Sponsor as soon as it is available or at least within 24 hours of the information becoming available. Events will be followed up until the event has resolved or a final outcome has been reached.”

All SAEs assigned by the CI/PI or delegate as both suspected to be related to IMP-treatment and unexpected will be classified as SUSARs and will be subject to expedited reporting to the Medicines and Healthcare Products Regulatory Agency (MHRA). The sponsor will inform the MHRA, the REC and Marketing Authorisation Holder of SUSARs within the required expedited reporting timescales.

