CRF	Case Report Form
CRO	Contract Research Organisation
CTA	Clinical Trial Authorisation
CTIMP	Clinical Trial of Investigational Medicinal Product
CTU	Clinical Trials Unit
DMC	Data Monitoring Committee
DSUR	Development Safety Update Report
EC	European Commission
EMA	European Medicines Agency
EU	European Union
EUCTD	European Clinical Trials Directive
EudraCT	European Clinical Trials Database
EudraVIGILANCE	European database for Pharmacovigilance
GCP	Good Clinical Practice
GMP	Good Manufacturing Practice
IB	Investigator Brochure
ICF	Informed Consent Form
ICH	International Conference on Harmonisation of technical requirements for registration of pharmaceuticals for human use.
IMP	Investigational Medicinal Product

EudraCT number: 2021-000071-36

SHORT TITLE: DORA

IMPD	Investigational Medicinal Product Dossier
ISF	Investigator Site File (This forms part of the TMF)
ISRCTN	International Standard Randomised Controlled Trials Number
MA	Marketing Authorisation
MHRA	Medicines and Healthcare products Regulatory Agency
MS	Member State
NHS R&D	National Health Service Research & Development
NIMP	Non-Investigational Medicinal Product
PD	Pharmacodynamics
PE	Pre-eclampsia
PI	Principal Investigator
PIC	Participant Identification Centre
PIS	Participant Information Sheet
PK	Pharmacokinetics
QA	Quality Assurance
QC	Quality Control
QP	Qualified Person
RCT	Randomised Control Trial
REC	Research Ethics Committee
SA	Salicylic Acid
SAE	Serious Adverse Event
SAR	Serious Adverse Reaction
SDV	Source Data Verification
SOP	Standard Operating Procedure
SmPC	Summary of Product Characteristics

SHORT TITLE: DORA

EudraCT number: 2021-000071-36

SSI	Site Specific Information
SUSAR	Suspected Unexpected Serious Adverse Reaction
Tbx B ₂	Thromboxane B ₂
TMF	Trial Master File
TMG	Trial Management Group
TSC	Trial Steering Committee

SHORT TITLE: DORA

EudraCT number: 2021-000071-36

Trial Title	A randomised crossover design study comparing the pharmacokinetics and pharmacodynamics of two single oral doses of aspirin (75 mg v150mg) in pregnant women at risk of pre-eclampsia.
Internal ref. no. (or short title)	DORA
Clinical Phase	NA
Trial Design	A randomised 2 x 2 crossover design
Trial Participants	Pregnant women at risk of preeclampsia with clinical indication for aspirin prophylactic therapy.
Planned Sample Size	14
Treatment duration	Single dose in 24 hours on two occasions one week apart
Follow up duration	24 hours
Planned Trial Period	01/03/2021 to 31/08/2021

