7.7 TRIAL ASSESSMENTS

- Screening for eligibility
- Invitation letter sent to eligible women
- Routine ultrasound
- Routine antenatal medical review
- Consent
- Eligibility checklist

EudraCT number: 2021-000071-36

SHORT TITLE: DORA

Visit 1	Visit 2	Wash out period 7 days (no aspirin until visit 3)	Visit 3	Visit 4	
Confirmation of consent	Assessment of AR/AE			Confirmation of consent	Assessment of AR/AE
Randomisation	Confirmation of consent			Compliance with the washout period check by the pill count	Confirmation of consent
Background data collection	Cannulation and sample at 15 hours			Cannulation and Sample 0	Cannulation and sample at 15 hours
Cannulation and Sample 0	Sample at 16 hours			First aspirin + meal	Sample at 16 hours
First aspirin + meal	Sample at 17 hours			Assessment of AR/AE	Sample at 17 hours
Assessment of AR/AE	Meal			Sample at 1 hour	Meal
Sample at 1 hour	Sample at 18 hours			Sample at 2 hours	Sample at 18 hours
Sample at 2 hours	Sample at 19 hours and discharge home			Sample at 3 hours	Sample at 19 hours and discharge home
Sample at 3 hours				Sample at 4 hours and discharge home	End of trial
Sample at 4 hours and discharge home					

EudraCT number: 2021-000071-36

SHORT TITLE: DORA

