9.7 REPORTING URGENT SAFETY MEASURES

If any urgent safety measures are taken the CI/Sponsor shall immediately and in any event no later than 3 days from the date the measures are taken, give written notice to the MHRA and the relevant REC of the measures taken and the circumstances giving rise to those measures.

9.8 THE TYPE AND DURATION OF THE FOLLOW-UP OF PARTICIPANTS AFTER ADVERSE REACTIONS.

Bedside observations will be performed for a duration of 4 hours post IMP ingestion.

Self-reported wellbeing check will be conducted at 20 hours post IMP ingestion.

In case of any (S)ARs, follow up care will be given until resolution.

For the duration of participation in the trial, any SUSAR will need to be reported to the Sponsor irrespective of how long after IMP administration the reaction has occurred until resolved.

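### Safety follow-up is stated to run to 24 h after dosing, but 9.8 sets the last self-report at 20 h, 7.7 lists nothing after 19 h, and no enquiry about washout events is listed before the second dose

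*Protocol*

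**What the plan says.** **End of follow-up.** Section 9.3 states: "Safety monitoring will be performed during the trial visits and end at 24 hours post last study dose ingestion". The synopsis gives "Follow up duration" as 24 hours. Section 7.8 says: "Trial participants will not be monitored after the active treatment phase has finished (24 hours post aspirin ingestion". The risk table in Appendix 1 lists, for each dose, a 4 h observation and a 24 h follow-up, and the text below it mentions a 24 h review again. It gives neither a mode of contact nor a visit.

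**Contacts for completers.** In 7.7, the visit 2 and visit 4 columns each finish with "Sample at 19 hours and discharge home". Section 9.8 adds 4 h of bedside observation and then: "Self-reported wellbeing check will be conducted at 20 hours post IMP ingestion". The 20 h check does not appear in 7.7.

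**Contacts for women who withdraw.** Section 9.3: "Where a participant withdraws consent safety assessments will be performed at 24 hours post aspirin ingested at the research visit".

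**Visit 3.** The 7.7 column lists confirmation of consent, "Compliance with the washout period check by the pill count", cannulation with sample 0, "First aspirin + meal", and only then the adverse reaction and event assessment. Table 1, which covers visits 1 and 2 and visits 3 and 4, ticks eligibility before aspirin. Section 9.4 gives the investigator a general duty to check for adverse events when participants attend.

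**The concern.** There are two separate gaps, both in the conduct of safety follow-up.

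1. The stated end of follow-up and the scheduled contacts do not match. Staff working from 7.7 have nothing to do after 19 h, and staff working from 9.8 make their last contact at 20 h. Only the appendix sends anyone to a completer at 24 h. Women who withdraw, by contrast, have a dated 24 h assessment in the body text.

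2. Section 9.3 has serious adverse events recorded from the start of treatment until 24 h after it stops, so the washout falls inside the recording window. Yet after the follow-up of dose 1, the next adverse event enquiry listed in 7.7 comes after dose 2. An event that began in the washout could be elicited only once the woman has been dosed again. Bleeding is the hazard named in Appendix 1, so it is the obvious thing to ask about before re-dosing.

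**Working it through.** The protocol gives no figure to reproduce here. The check sets the sections side by side and subtracts time points.

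**Inputs**

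| Source | Time after dose | Nature |
|---|---|---|
| Synopsis, 7.8, 9.3 | 24 h | stated end of follow-up or monitoring |
| Appendix 1 | 24 h | follow-up listed as an activity, each dose |
| 9.3, withdrawals only | 24 h | safety assessment |
| 9.8 | 20 h | self-reported check |
| 7.7, visits 2 and 4 | 19 h | last sample, then discharge |
| 8.6 | 1 week | interval between doses |

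**Gap 1: shortfall for a completer = stated end − last contact**

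- By 9.8: 24 − 20 = 4 h.
- By 7.7 alone: 24 − 19 = 5 h.
- If the Appendix 1 follow-up is carried out: 24 − 24 = 0 h.
- For a woman who withdraws (9.3): 24 − 24 = 0 h.

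The 20 h check is the last dated contact for a completer in the body text, so 4 h is the relevant shortfall when the appendix is not used.

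**Gap 2: time before dose 2 with no listed enquiry**

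- Dose interval: 7 × 24 = 168 h. With dose 1 on day 1, dose 2 falls on day 8 and the last sample on day 9, which agrees with the 9-day participation in section 7.
- From the 20 h check to dose 2: 168 − 20 = 148 h.
- From a 24 h follow-up to dose 2: 168 − 24 = 144 h.

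**What is asked before dose 2.** Dose 1 is followed by an assessment at visit 1, another at visit 2 and the 20 h check, plus the Appendix 1 follow-up if done. All of these fall within 24 h of dose 1. For events starting later, Table 1 offers a pre-dose eligibility check, but it has no adverse event row. Section 9.4 requires a check at attendance without placing it before or after the dose. The visit 3 column of 7.7 places it after.

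**The case against.** The strongest reply to the first gap is that a recording window is not a scheduled contact. The synopsis, 7.8 and 9.3 could simply say how long events count, and a window may outlast the last visit, especially as Appendix 1 provides emergency contacts. That would be a fair reading of those three places alone. It does not explain Appendix 1, which lists the 24 h follow-up as an activity after each dose, or why 9.8 puts the corresponding self-report at 20 h.

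On the second gap, the pre-dose eligibility tick in Table 1 carries weight: the exclusion criteria in 6.2 cover aspirin hypersensitivity, gastrointestinal haemorrhage and other bleeding, so a repeat check could catch the most important reactions. The duty in 9.4 also applies at visit 3. For serious events, 9.3 collects start and end dates and causality, so a late report would still be dated to the washout. These points reduce the gap. They do not place an adverse event enquiry before the dose.

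Three stronger readings are tempting and are not supported:

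- A reader might infer that the second dose could be given before anyone asks about a reaction to the first. The assessments at visits 1 and 2 and the 20 h check all come before dose 2. Only events starting after those contacts are left without a listed enquiry.
- A reader might infer from the order of items in 7.7 that adverse event enquiry ends before the 15 h sample, 24 − 15 = 9 h short of the window. That rests on list order in an untimed column, whereas 9.3 says monitoring takes place during the visits.
- A reader might infer that completers have no 24 h contact at all. Appendix 1 plans one.

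**Conclusion.** The point holds as a minor inconsistency in safety conduct. A completer's last dated contact in the body text is 4 h short of the stated 24 h, and the shortfall is zero if Appendix 1 is followed. At visit 3, no adverse event enquiry about the washout is listed before dosing, which leaves a nominal 144 to 148 h uncovered by the schedule in 7.7.

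This rests on two assumptions: that the visit 3 column of 7.7 reads in time order around the dose, as its sequence of sample 0, dose and 1 to 4 h samples suggests; and that doses are 168 h apart, as 8.6 states. The clinical risk is low, since the exposure is two observed single doses of aspirin in clinical use. The two AUC endpoints and their analysis are not affected.

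**What to change.** - In 9.8, move the self-reported check from 20 h to 24 h, so that it becomes the follow-up listed in Appendix 1.
- In 7.7, list that contact after each dose: once after visit 2, and once after visit 4 ahead of the end-of-trial mark.
- In the visit 3 column of 7.7, add an adverse reaction and event assessment covering events since visit 2, placed before the aspirin. Keep the existing post-dose assessment.

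The cost is negligible. One existing self-report moves by 4 h, and one question is added at a visit already planned. No extra visit or blood sample is needed.

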9.4 RESPONSIBILITIES

Principal Investigator (PI):

Checking for AEs and ARs when participants attend for treatment / follow-up.

Using medical judgement in assigning seriousness, causality and whether the event/reaction was anticipated using the SmPC.

Ensuring that all SAEs are recorded and reported to the sponsor within 24 hours of becoming aware of the event and provide further follow-up information as soon as available. Ensuring that SAEs are chased with Sponsor if a record of receipt is not received within 2 working days of initial reporting.

Ensuring that AEs and ARs are recorded and reported to the sponsor in line with the requirements of the protocol.

Chief Investigator (CI) / delegate or independent clinical reviewer:

EudraCT number: 2021-00071-36

SHORT TITLE: DORA

Clinical oversight of the safety of patients participating in the trial, including an ongoing review of the risk / benefit.

Using medical judgement in assigning the SAEs seriousness, causality and whether the event was anticipated (in line with the SmPC) where it has not been possible to obtain local medical assessment.

Immediate review of all SUSARs.

Review of specific SAEs and SARs in accordance with the trial risk assessment and protocol as detailed in the Trial Monitoring Plan.

Assigning Medical Dictionary for Regulatory Activities (MedDRA) or Body System coding to all SAEs and SARs.

Preparing the clinical sections and final sign off of the Development Safety Update Report (DSUR).

Sponsor:

Central data collection and verification of AEs, ARs, SAEs, SARs and SUSARs according to the trial protocol onto a database.

Reporting safety information to the CI, delegate or independent clinical reviewer for the ongoing assessment of the risk / benefit according to the Trial Monitoring Plan.

Reporting safety information to the independent oversight committees identified for the trial (Data Monitoring Committee (DMC) and / or Trial Steering Committee (TSC)) according to the Trial Monitoring Plan.

Expedited reporting of SUSARs to the Competent Authority (MHRA in UK) and REC within required timelines.

Notifying Investigators of SUSARs that occur within the trial.

Checking for (annually) and notifying PIs of updates to the Reference Safety Information for the trial.

Preparing standard tables and other relevant information for the DSUR in collaboration with the CI and ensuring timely submission to the MHRA and REC.

Trial Management Group (TMG)

TMG will act as TSC and meet at agreed time points to review safety data to determine patterns and trends of events, or to identify safety issues (in accordance with the Trial Terms of Reference for the TSC).

SHORT TITLE: DORA

EudraCT number: 2021-000071-36

